Study products were then dispensed to the subject with both written and verbal instructions for use and the Diary Usage Form. Toothpaste tubes and oral rinse bottles were weighed prior to dispensing, with weights recorded on the data collection form. Dispensed products included two 32-ounce bottles of CloSYS Sensitive oral rinse and two 7-ounce tubes of CloSYS Sensitive fluoride toothpaste and disposable dosing cups. The PI provided both verbal and written oral hygiene instructions as follows:

- Clean between the teeth using dental floss or a proxy brush
- Brush with CloSYS Sensitive fluoride toothpaste for 2 minutes twice daily. Subjects were permitted to brush with either a manual or power toothbrush according to individual preference.
- After brushing, rinse with 15 mL CloSYS Sensitive oral rinse for 30 seconds, then expectorate. Do not eat or drink for 30 minutes after rinsing.

Subjects also received a Diary Usage Form with instructions to complete the form daily. Subjects documented brushing and rinsing behaviors, including the time and date for each brushing/rinsing event. Subjects were also instructed not to use any other oral care products than those given as part of the study during the entire study period. Subjects were instructed to bring back their toothpaste tubes and oral rinse bottles at each subsequent study visit along with the

Diary Usage Form. Self-reported product use and remaining product weight were used to assess compliance with the study regimen.

The subject then received an oral prophylaxis and was scheduled to return in 6 weeks for a follow-up study appointment (Visit 2).

Subjects returned for 2 additional study visits, scheduled every 45 days (Visit 2, Day 45; Visit 3, Day 90).

At Visit 2 (Day 45), subjects received photos and MGI, PI. The presence/absence of adverse events was assessed and documented. The completed Diary Usage Form and remaining products were collected, and products were weighed, with weights recorded on the data collection form. A new Diary form, one new tube of toothpaste, one new bottle of oral rinse and disposable dosing cups were dispensed with instructions to return the form and remaining products at the final study visit (Visit 3).

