At Visit 3 (90 days), subjects received photos, MGI, PI, PD, CAL, BOP. Remaining products were collected and weighed, with weights recorded on the data collection form. The Diary Usage Form was also collected. The presence/absence of adverse events was assessed and documented. Subjects completed a brief survey about their product use experience and preferences (ease of use, taste, willing to continue regimen, willing to purchase).

The presence or absence of adverse events (yes/no) was documented at each study visit on the data collection form. Adverse events that occurred were described and recorded by the PI on the Adverse Events form. If indicated, photographs were taken and appropriate reporting was made to the ATSU IRB and Study Sponsor according to the study protocol and university policies.

For Visits 2 and 3, compliance was scored as a dichotomous variable (yes/no). Compliance was scored as “yes” if product weights decreased upon return and if self-reported product use according to the study protocol was completed 90% of the time as documented on the returned Diary Usage Form.

At the end of the final study visit, each subject who completed the study in its entirety was given a \$50 Amazon gift card as a reward for successful study completion.

Summary of Study Visits

- Screening exam/Consent
- Visit 1(0 Days) = Baseline
 - ✓ Updated medical history
 - ✓ Photos/Indices (MGI, PI, PD, CAL, BOP)
 - ✓ Dispensed Products
 - ✓ Provided Verbal and Written Oral Hygiene Instructions and Diary
- Prophylaxis provided by dental hygienist
- Visit 2 (45 days)
 - ✓ Updated medical history
 - ✓ Photos/Indices (MGI, PI)

- ✓ Assessed adverse events
- ✓ Collected unused product which was weighed for compliance
- ✓ Collected Diary was reviewed for compliance
- ✓ Dispensed Products and Diary
- Visit 3 (90 days)
 - ✓ Updated medical history
 - ✓ Photos/Indices (MGI, PI, PD, CAL, BOP)
 - ✓ Assessed adverse events
 - ✓ Collected unused product which was weighed and reviewed for compliance
 - ✓ Collected Diary was reviewed for compliance
 - ✓ Subject product use experience and preferences survey completed
 - ✓ Dispensed \$50 gift card reward

Removal of Subjects

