Data was coded and entered into an Excel spreadsheet which was then imported into IBM SPSS version 28 for analysis. Descriptive statistics were used to report demographics. The Kruskal-Wallis test, with the Dunn post-hoc test, was used to compare MGI and PI at baseline, 6 weeks and 12 weeks. Pairwise comparisons using Wilcoxon signed rank test was used to compare differences in bleeding on probing (BOP) between baseline and 12 weeks. Adverse events data, compliance data and patient product use experience data were reported using descriptive statistics. All data were de-identified and reported in aggregate form only.

REFERENCES

2. Bosshardt DD. The periodontal pocket: pathogenesis, histopathology and consequences. *Periodontol 2000*. 2018 Feb;76(1):43-50. doi: 10.1111/prd.12153. Epub 2017 Nov 30.
5. Gunsolley JC. Clinical efficacy of antimicrobial mouthrinses. *J Dent*. 2010 Jun;38 Suppl 1:S6-10. doi: 10.1016/S0300-5712(10)70004-X. Review.
8. Löe H. The Gingival Index, the Plaque Index and the Retention Index Systems. *J Periodontol*. 1967 Nov-Dec;38(6):Suppl:610-6.
9. Bessa-Rebelo M, Corrêa de Queiroz, A. Gingival Indices: State of the Art. Available at: https://www.researchgate.net/profile/Maria_Rebelo2/publication/221917002_Gingival_Indices_State_of_Art/links/544658a10cf2f14fb80f32ad/Gingival-Indices-State-of-Art.pdf Accessed January 15, 2020.

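### The weight half of the compliance rule sets no minimum, so the 90% standard rests on the self-reported diary alone

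*Combined protocol and SAP*

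**What the plan says.** The scoring rule is in Study Procedures. Compliance at Visits 2 and 3 is a yes/no variable, and it is yes "if product weights decreased upon return and if self-reported product use according to the study protocol was completed 90% of the time", as shown on the returned diary form. The same section describes the two sources as working together: "Self-reported product use and remaining product weight were used to assess compliance with the study regimen".

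The material for a quantitative check is partly there. For Visit 1, "Toothpaste tubes and oral rinse bottles were weighed prior to dispensing, with weights recorded on the data collection form". The supply is stated: "Dispensed products included two 32-ounce bottles of CloSYS Sensitive oral rinse and two 7-ounce tubes" of toothpaste. The rinse dose is fixed: "After brushing, rinse with 15 mL CloSYS Sensitive oral rinse for 30 seconds, then expectorate". Returned product is weighed and recorded at Visits 2 and 3, and the Visit 3 list in Summary of Study Visits has "Collected unused product which was weighed and reviewed for compliance". The diary is detailed: "Subjects documented brushing and rinsing behaviors, including the time and date for each brushing/rinsing event".

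Study Outcomes names compliance as a secondary outcome. Statistical Analysis limits it to description: "Adverse events data, compliance data and patient product use experience data were reported using descriptive statistics". Nowhere do the documents give an expected weight loss, a minimum decrease, a comparison of weights with diary counts, or a plan to report the amount used.

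**The concern.** A product weight is the only measure of use here that does not depend on what the subject reports. Its natural purpose is to catch a diary that claims more use than took place. Under the stated rule it does so only when a product was not used at all, because any decrease is enough.

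A compliance rate described as resting on both diary and weights would suggest more verification than the rule supplies. This matters for interpretation because all three hypotheses concern subjects who use the products as directed, and the study is non-blinded and self-controlled. A reader would want to know whether reported adherence is supported by something other than self-report.

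**Working it through.** The plan gives no expected use or minimum weight, so there is no stated figure to reproduce beyond the 90% diary standard.

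**Inputs from Study Procedures:** visits every 45 days; brushing twice daily; a 15 mL rinse after brushing; two 32-ounce rinse bottles issued at Visit 1. **Assumptions:** US fluid ounces (29.5735 mL) and 1 g/mL. The empty container's weight cancels in dispensed minus returned.

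**Uses due per product, one period**
- 45 × 2 = 90. Diary standard: 0.9 × 90 = 81.
- Smallest use that lowers the weight: 1/90 = 1.1%. Taking the interval as 6 weeks (42 days): 1/84 = 1.2%.
- If each of the two bottles and two tubes must weigh less: 2/90 = 2.2%.

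**Rinse, Visit 1 to Visit 2**
- Due: 90 × 15 = 1,350 mL. Issued: 64 × 29.5735 = 1,893 mL, so supply exceeds the amount due.
- Half use: 675 mL used, 1,893 − 675 = 1,218 mL returned.
- 90% use: 81 × 15 = 1,215 mL used, 1,893 − 1,215 = 678 mL returned.
- Difference: 540 mL. Both subjects meet the weight condition.
- If the ounce is a weight ounce (28.35 g): issued 1,814 g, returned 1,139 g and 599 g, and the difference is still 540.

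**How a weight-based flag would behave**
- Flag levels: under 90% is under 1,215 mL; under 80% is under 1,080 mL. Half use (675 mL) is caught by both.
- Every rinse taken with a 13 mL pour: 90 × 13 = 1,170 mL = 86.7%, flagged at 90% but not at 80%.
- 81 rinses with a 13 mL pour: 81 × 13 = 1,053 mL = 78.0%, flagged at both.

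A flag therefore shows disagreement with the diary. It does not prove non-compliance.

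**Rinse, Visit 2 to Visit 3**
- Remaining products are collected at Visit 2 and one new bottle is issued. Its size is not stated, nor is whether leftovers were handed back.
- If it is 32 ounces and leftovers were kept by the site: 946 mL, and 946/1,350 = 70.1% of the amount due (946/1,260 = 75.1% over 42 days). Everyone with a diary at or above 90% would then be flagged at both levels, whatever they did.
- If leftovers were handed back after full use in the first period: 1,893 − 1,350 + 946 = 1,489 mL, which covers the period.

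The same flag is therefore informative in the first period but may be meaningless in the second.

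**The case against.** The strongest reply is that the rule is explicit and workable. Two conditions are joined by *and*, the 90% is openly placed on the diary, and the weight check is only coarse corroboration. A subject at 1.1% use still scores no unless the diary claims about 81 of 90 uses, each entered with time and date. This stands, and it confines the gap to over-reported diaries. It does not close the gap, because over-reporting is what an independent weight check is there to find.

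The 1.1% is also a boundary figure. It becomes 2.2% on the every-container reading, and a spill alone could lower the weight of a bottle with no use at all. None of these readings creates a meaningful minimum.

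Weights are noisy, and toothpaste has no specified amount per brushing, so half the regimen cannot be expressed as a percentage. That is a sound reason not to rescore anyone and to treat the figures as description.

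The second-period objection also stands: a pre-dispensing weight is documented only for Visit 1, and supply may have fallen short of the amount due. Any remedy has to be conditional there.

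Finally, the descriptive reporting of compliance data might already include the recorded weights. The documents neither say so nor rule it out, so the point is that the plan does not specify it, not that it was left out of the report.

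**Conclusion.** The point holds and is minor. As written, the weight condition can be met by about 1 of 90 uses per product (1.1%; 2.2% if every Visit 1 container must lose weight), and the 90% standard is enforced by self-report only. A subject who under-uses and over-reports is scored compliant. The 1.1% follows from the stated schedule; the returned rinse volumes rest on the fluid-ounce and density assumptions, but the 540 mL gap between half use and 90% use does not depend on which ounce is meant.

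A reader might go further and infer any of the following, none of which the documents support:
- *That the reported compliance rate is inflated.* Nothing shows how many diaries, if any, were over-reported.
- *That the efficacy findings are weakened.* Compliance defines no analysis set, triggers no exclusion and enters no test, so the plaque, gingival and bleeding analyses are unchanged.
- *That subjects could not have complied in the second period.* This needs both a 32-ounce bottle and leftovers not returned to the subject, and the documents settle neither.

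**What to change.** Keep the existing yes/no score, label it diary-based, and rescore no one. Then add the following, marked as post hoc:

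- **Visit 1 to Visit 2, rinse.** Report rinse used by weight as a percentage of 30 mL × actual days since dispensing (median and range), beside the diary percentage. Give the number of subjects with a diary at or above 90% but weight-based use under 90%, and under 80% as a sensitivity check for small pours.
- **Toothpaste.** Report grams used per day only.
- **Visit 2 to Visit 3, rinse.** Report the same percentage and flags only if the starting weight is known and either leftovers were handed back or the supply covered the period. Otherwise report rinse used without flags and state the supply limit. In either case, state the Visit 2 bottle size and what happened to leftovers.

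The cost is one paragraph and a descriptive calculation, on weights already recorded for the first period; the second period may first need the site to confirm supply and starting weights. There are downsides: reported compliance may look lower, small pours reduce the percentage, and spilled or shared rinse counts as use. No primary analysis changes.

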Subjects were given the right to withdraw from the study at any time and for any reason without prejudice to receiving future dental care at the institution. The PI documented the withdrawal/removal from the study and the reason for withdrawal/removal in the study record. If a subject experienced a complication and wanted to withdraw, if they consented, they were scheduled for an immediate follow-up/closeout examination to determine if an adverse event was present, and if so, the causation of the adverse event was recorded. Every effort was made to follow-up with subjects who withdrew on their own from the study.

Subject data only up to the time when the subjects were withdrawn was kept but was not included in the data analysis of the study.

Off Study

Subjects were considered off study when all planned study visits, early termination, and follow-up visits were completed.

Study Outcomes

This study assessed differences in clinical outcomes at baseline, 6 and 12 weeks. The primary outcomes include changes in gingival and plaque indices (GI and PI, respectively), and bleeding on probing. Because enrolled subjects presented primarily with gingivitis, changes in pocket depth and clinical attachment level were not included in the initial data analysis, as clinically, changes observed were negligible. Secondary outcomes included adverse events, compliance with the oral hygiene regimen and patient product use experience and preferences data.

14. Hypotheses

The hypotheses for the study were as follows:

- Subjects who apply CloSYS Sensitive fluoride toothpaste and Sensitive oral rinse as directed will experience reductions in PI across time.
- Subjects who apply CloSYS Sensitive fluoride Toothpaste and Sensitive oral rinse as directed will experience reductions in GI across time.
- Subjects who apply CloSYS Sensitive fluoride Toothpaste and Sensitive oral rinse as directed will experience reductions in BOP across time.

Statistical Analysis

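### As written, the rule that drops withdrawn subjects' data from the analysis also removes them from the adverse event summary, because no safety population or exception is stated

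*Combined protocol and SAP*

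**What the plan says.** All references are to the combined protocol and SAP.

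- **Removal of Subjects** sets the rule: "Subject data only up to the time when the subjects were withdrawn was kept but was not included in the data analysis". The sentence concerns subject data in general and names no exception.
- The same section provides for a subject who has a complication, wants to withdraw and consents: "they were scheduled for an immediate follow-up/closeout examination to determine if an adverse event was present". Causation is recorded if an event is found. It also says "The PI documented the withdrawal/removal from the study and the reason for withdrawal/removal in the study record", and "Every effort was made to follow-up with subjects who withdrew on their own from the study".
- **Study Outcomes** lists what the rule could touch: "Secondary outcomes included adverse events, compliance with the oral hygiene regimen and patient product use experience and preferences data".
- **Study Procedures** describes collection: "The presence or absence of adverse events (yes/no) was documented at each study visit on the data collection form", and "Adverse events that occurred were described and recorded by the PI on the Adverse Events form". Where indicated, "appropriate reporting was made to the ATSU IRB and Study Sponsor according to the study protocol and university policies". Compliance is scored yes or no at Visits 2 and 3. The Modified Gingival Index and the Plaque Index are measured at Visit 2 (Day 45).
- **Statistical Analysis** says that adverse events, compliance and product experience are summarised with descriptive statistics. It names no analysis set for any of them.
- **Number of Subjects** gives 60, without saying whether that is the number enrolled or the number who completed. No section gives a count of withdrawals or of adverse events.

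**The concern.** Excluding people who leave is a doubtful choice for efficacy and a worse one for safety, because an adverse event can itself be the reason for leaving. The plan foresees this: it arranges an examination for subjects who want to withdraw after a complication. If the general exclusion then applies to what that examination finds, the safety summary is restricted to the people who tolerated the products well enough to stay.

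At stake is the adverse event rate of a single-arm study that has no comparator to set it against. If withdrawn subjects had more events than those who stayed, the reported rate understates harm. If they had none, it is slightly too high. From the documents a reader cannot tell which.

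The same sentence has two lesser effects. A subject who left between Day 45 and Day 90 may have a Visit 2 compliance score and Day 45 index scores on record, and neither is used.

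**Working it through.** **Step 1: does the rule reach the adverse event summary?** The documents state no figure to reproduce, so the first check sets the sections side by side.

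- The rule removes withdrawn subjects' data from the study's data analysis (Removal of Subjects).
- Adverse events and compliance are outcomes of the study (Study Outcomes).
- Their summaries are described under Statistical Analysis.
- No section gives a different population for them.

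Together these put the adverse event summary inside the exclusion. This is the plain reading; no sentence says it of adverse events expressly.

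**Step 2: do the excluded data exist?** Yes, for any subject who withdrew after a visit or had a closeout examination. Adverse events are recorded at each visit and at closeout, compliance is scored at Visit 2, and data up to withdrawal are kept.

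**Step 3: how large could the effect be?** The only input from the documents is 60. The rest is assumed:

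- W = number withdrawn
- x = subjects with an event among those who stayed
- e = subjects with an event among those who withdrew

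If the 60 were enrolled:

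- reported rate = x / (60 − W)
- rate over all enrolled = (x + e) / 60
- the report is too low when e > x·W / (60 − W)

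Intervals are exact (Clopper-Pearson) 95%.

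| Assumed W, x, e | Reported | Over all enrolled | Report is |
|---|---|---|---|
| 6, 0, 3 | 0/54 = 0% (0 to 6.6) | 3/60 = 5.0% (1.0 to 13.9) | 5.0 points too low |
| 6, 3, 0 | 3/54 = 5.6% (1.2 to 15.4) | 3/60 = 5.0% (1.0 to 13.9) | 0.6 points too high |
| 6, 3, 1 | 3/54 = 5.6% (1.2 to 15.4) | 4/60 = 6.7% (1.8 to 16.2) | 1.1 points too low |

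For W = 6 and x = 3 the threshold is 3 × 6 / 54 = 0.33, so a single event among the six withdrawn subjects is enough to make the report too low.

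If instead 60 completed and 6 more withdrew, with three events in each group, the report reads 3/60 = 5.0% (1.0 to 13.9) against (3 + 3)/66 = 9.1% (3.4 to 18.7). This is why the meaning of the 60 matters.

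**Step 4: Visit 2 compliance.** Assume 49 of 54 who stayed were compliant and 3 of 6 withdrawn subjects had attended Visit 2. The report reads 49/54 = 90.7%. Over everyone who attended Visit 2 it would lie between 49/57 = 86.0% (none of the three compliant) and 52/57 = 91.2% (all three compliant). Even the direction is open.

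No figure is offered for the Day 45 indices, because the documents give nothing from which to build one.

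**The case against.** The best counter-argument is that the exclusion was meant for efficacy only. Statistical Analysis names tests for the two indices and bleeding, then says separately that adverse events were reported descriptively, so the data analysis could be taken to mean the tests. The reading is possible, but nothing in the text supports it: the rule is worded for subject data in general, and the descriptive summaries sit under the same heading as the tests. What stands is that the omission is an inference from the plain wording, not an explicit statement about adverse events.

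A second argument is that the Off Study section treats early termination and follow-up visits as part of the study. It does, but it does not bring their findings into any summary.

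A third is that the information is protected. Events go on the Adverse Events form, reach the IRB and sponsor where indicated, and withdrawal reasons are documented. All of this stands. A reader might infer that adverse events of withdrawn subjects were lost or concealed, and the documents do not support that. The gap is in the aggregate summary.

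A reader might also take the statement that data were reported only in aggregate as proof that nobody outside sees these events. It reads more naturally as a confidentiality statement and sets no analysis population, so no weight is put on it here.

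Finally, every scenario is assumed and the intervals overlap widely. That stands too: the figures show what the rule can do, not what it did.

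**Conclusion.** The point holds as a defect in the written plan. Followed literally, the rule leaves withdrawn subjects out of the adverse event summary, including those who left after a complication.

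It would be tempting to conclude that the reported adverse event rate is too low. The documents do not support that. They give neither withdrawals nor events, the bias can run either way, and there is none if nobody withdrew. Under the assumptions shown with 60 enrolled, the discrepancy runs from 0.6 points too high to 5.0 points too low. The case that matters most is a reported zero when events did occur among those who left.

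The compliance and Day 45 parts follow from the same sentence but are minor and would not justify a change on their own. The change should be made, because the rule is explicit, the data are already held and the repair is cheap. Confidence is medium, because the reach of the rule is inferred and its effect depends on an unstated count.

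**What to change.** Keep the sentence in Removal of Subjects as the record of the original efficacy analysis, and add text along these lines:

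> Adverse events are summarised for every subject dispensed product, including events found before or at withdrawal and at the closeout examination. The number, timing and documented reasons of withdrawals are tabulated, and it is stated whether the 60 subjects were enrolled or completed.

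As secondary additions:

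- Report Visit 2 compliance for all subjects who attended Visit 2.
- As a supplementary analysis, labelled as added later, report Day 0 to Day 45 changes in the Modified Gingival Index and the Plaque Index for all subjects with both visits, beside the result without withdrawn subjects.

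If the exclusion was meant for efficacy only, the first sentence of the added text makes that clear.

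The cost is a short text addition, one withdrawal and adverse event table, one compliance line and one labelled supplementary result. No new data collection is needed, though withdrawn subjects' records may have to be entered in the analysis file. The downside for the sponsor is that the adverse event rate, or the supplementary Day 45 result, may look less favourable.

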At the Baseline appointment (Visit 1, Day 0), the Subject had a photograph taken of their mouth. The Gingival Index (GI) was measured first using the Modified Gingival Index (MGI).^{7,8,9} The severity of gingival inflammation was recorded from the buccal, lingual and interproximal aspects of all evaluable teeth as follows:

- Score 0 = absence of inflammation
- Score 1 = mild inflammation or with slight changes in color and texture but not in all portions of the gingival margin or papilla
- Score 2 = mild inflammation, such as the preceding criteria, in all portions of the gingival margin or papilla
- Score 3 = moderate, bright surface inflammation, erythema, edema and/or hypertrophy of the gingival margin or papilla
- Score 4 = severe inflammation: erythema, edema and/or marginal gingival hypertrophy of the unit or spontaneous bleeding, papillary congestion or ulceration

MGIs were determined by visual exam of the gingiva on 4 surfaces for each tooth present except for third molars, for a total of 28 teeth. The total number of teeth exhibiting inflammation affecting all portions of the gingival unit (Score ≥ 2) were noted at each visit. The total number of teeth affected was evaluated for each visit in the final analysis.

Next, the Plaque Index (PI) was recorded on all teeth except for third molars, as originally described by Silness and Löe.^{10,11} The PI was recorded on 4 surfaces of each tooth and scored as follows:

- Score 0 = No plaque in gingival area
- Score 1 = No plaque visible by the unaided eye, but plaque is made visible on the point of the probe after it has been moved across surface at entrance of gingival crevice.
- Score 2 = Gingival area is covered with a thin to moderately thick layer of plaque; deposit is visible to the naked eye
- Score 3 = Heavy accumulation of soft matter, the thickness of which fills out niche produced by gingival margin and tooth surface: interdental area is stuffed with soft debris

To calculate the Plaque Index (PI), the four scores were summed for each tooth, and then all scores for all of the teeth present in a subject's mouth were added to determine a total score. Then, the total score was then divided by the number of surfaces to yield the percentage plaque score used in the final analysis.

Results of the clinical indices were recorded on the approved data collection form by the PI.

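### Subjects scored for MGI and PI at Day 0 and Day 45 who withdraw before Day 90 are dropped from the baseline-to-6-week comparison because of a later event

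*Combined protocol and SAP*

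**What the plan says.** The Removal of Subjects section sets no limit on when or why a subject may leave: "Subjects were given the right to withdraw from the study at any time and for any reason". It then states how their data were handled: what had been collected up to withdrawal "was kept but was not included in the data analysis of the study".

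Study Procedures gives the visits: "Subjects returned for 2 additional study visits, scheduled every 45 days (Visit 2, Day 45; Visit 3, Day 90". MGI and PI were scored at Day 0, Day 45 and Day 90. BOP was scored at Day 0 and Day 90 only.

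Study Outcomes names the gingival index, the plaque index and BOP as primary. Under Statistical Analysis, the Kruskal-Wallis test with Dunn post-hoc comparisons "was used to compare MGI and PI at baseline, 6 weeks and 12 weeks", and BOP is compared between baseline and 12 weeks by the Wilcoxon signed rank test. That section defines no analysis set, no missing-data method and no sensitivity analysis that would bring the excluded scores back.

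**The concern.** The baseline-to-6-week change in MGI and PI is fully observed once a subject has attended Visit 2. Under the exclusion rule, whether that change counts depends on whether the subject later withdraws. The Day 45 result is thus conditioned on an event after Day 45, although the scores exist and were kept.

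The study has one group and each subject is their own control, so no second arm could partly offset such selection. If those who left between Day 45 and Day 90 had improved less than those who stayed, the reported 6-week reduction is too large. If they had improved more, it is too small.

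**Working it through.** The plan gives no figure to reproduce: it states no dropout rate, standard deviation or effect size. The check has two parts.

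**1. Reading the rule against the schedule, for a subject who withdraws between Day 45 and Day 90**

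| Outcome | Scores held | Usable without the rule | Used under the rule |
|---|---|---|---|
| MGI, PI: baseline to Day 45 | Day 0 and Day 45 | Yes, complete pair | No |
| MGI, PI: baseline to Day 90 | Day 0 only | No Day 90 value exists | No |
| BOP: baseline to Day 90 | Day 0 only | No, the paired test needs Day 90 | No |

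Only the first row loses a usable comparison through the rule. The planned test does not force the loss: Kruskal-Wallis treats the visits as separate groups and does not need complete cases.

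**2. Illustrative size at Day 45**

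Inputs:
- N = 60, from Number of Subjects. The plan does not say whether 60 were enrolled or completed. Here 60 is taken as enrolled, with all 60 scored at Day 45.
- w = number who withdraw after Day 45. Assumed: 5%, 10%, 15% or 20% of 60, that is 3, 6, 9 or 12.
- g = difference in mean Day 45 change between completers and leavers, in SD units. Assumed: 0.25, 0.5 or 1.0.

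With completer mean C and leaver mean L, the mean over everyone scored is ((N − w)C + wL)/N. The rule reports C. The shift is

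C − ((N − w)C + wL)/N = (w/N)(C − L) = (w/N) × g.

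| w of 60 | Analysed | Scored values dropped per index (2w) | g = 0.25 | g = 0.5 | g = 1.0 |
|---|---|---|---|---|---|
| 3 (5%) | 57 | 6 | 0.0125 | 0.025 | 0.05 |
| 6 (10%) | 54 | 12 | 0.025 | 0.05 | 0.10 |
| 9 (15%) | 51 | 18 | 0.0375 | 0.075 | 0.15 |
| 12 (20%) | 48 | 24 | 0.05 | 0.10 | 0.20 |

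The range is about 0.01 to 0.20 SD. Using every Day 45 pair removes this shift. The planned tests are rank-based, so a shift in a mean is an illustration and not the effect on the test statistic.

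If 60 is instead the number of completers, enrolment at the same dropout rates would have been 64 (60/0.95), 67 (60/0.90), 71 (60/0.85) or 75 (60/0.80), each rounded up. The shift depends only on the fraction w/N, so its range is essentially unchanged.

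**The case against.** **No withdrawals may have occurred, and the direction of bias is unknown.** This stands. With none there is no effect, and the documents do not say why anyone left.

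**The hypotheses concern subjects who use the products as directed, so those who stayed are the relevant group.** This does not justify the rule, which selects on withdrawal and not on adherence. Compliance is scored separately at Visits 2 and 3, and no non-compliant subject is excluded for it. A non-compliant completer stays in, while a subject compliant to Day 45 who leaves on Day 60 is out.

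**The rule tends to keep the same people at every visit.** This has force against simply restoring all scores. Under an unpaired Kruskal-Wallis test, leavers would enter the baseline group but not the Day 90 group, mixing change with a change in who is measured. The remedy must therefore be a within-subject comparison.

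A reader might infer more than the documents support:

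- *All three primary outcomes are inflated by the rule.* The rule removes no usable BOP pair and no Day 90 value. Selection at Day 90 is a missing-data problem that exists with or without the sentence.
- *The reductions could be overstated by up to 25%.* That figure follows if 20% leave and leavers do not improve at all, since 1/(1 − 0.20) − 1 = 0.25. It compares completers with all enrolled, so it does not measure the Day 45 effect. Zero change is also extreme, because every subject was due a prophylaxis after the baseline scoring.
- *The investigator could select the analysed subjects by removal.* The section says "The PI documented the withdrawal/removal from the study and the reason for withdrawal/removal in the study record", and Study Procedures says "Results of the clinical indices were recorded on the approved data collection form by the PI", in a non-blinded study. No removal criterion is stated. But the exclusion sentence speaks of withdrawn subjects; its extension to removed ones is inferred from the heading and neighbouring wording. Nothing shows that any removal depended on scores.
- *Indices were deliberately omitted at close-out.* The text describes a "follow-up/closeout examination to determine if an adverse event was present". It is silent on whether indices were taken.

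**Conclusion.** The point holds for MGI and PI at Day 45. The plan states a rule, not merely an omission, under which complete baseline-to-6-week pairs are discarded because of later withdrawal, and nothing in Statistical Analysis restores them. The resulting estimate describes subjects who stayed and can be biased either way.

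The shift of about 0.01 to 0.20 SD in the mean Day 45 change rests on two assumptions that the documents cannot confirm: that 5% to 20% left after Day 45, and that they differed from completers by 0.25 to 1.0 SD. The point does not extend to the BOP test, and it does not show that the Day 90 reductions are overstated by any given amount. The change is worth making because it concerns primary outcomes and the scores needed were kept.

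**What to change.** 1. For MGI and PI, replace the exclusion sentence with: scores recorded up to withdrawal or removal are included in the efficacy analysis.
2. Compare baseline with Day 45 within subject, in everyone scored at both visits, whatever happened later. The Wilcoxon signed rank test, which the plan already uses for BOP, would serve.
3. For Day 90 MGI, PI and BOP, report the paired observed result. Add, only as a deliberately conservative sensitivity analysis, one that assigns no change from baseline to subjects without a Day 90 score. Note beside it that it may understate the reduction, because of the prophylaxis after baseline scoring.
4. Report the number, timing and reasons of withdrawals and removals, and say whether 60 is the number enrolled or completed.

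Cost: one reworded sentence and a small re-analysis of data already kept. The numbers of subjects at Day 45 and Day 90 may differ and must be shown, and the reported reductions may be slightly smaller. The document describes the study as already carried out, so adding index scoring at close-out visits is not part of this fix.
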